#### **1.4. Rationale for SEL24/MEN1703 Starting Dose Selection and Dose Escalation Plan**

The first-in-human (FIH) starting dose for the clinical study in patients with AML was derived based on data accumulated from preclinical non-GLP and GLP repeat oral dose toxicology studies with SEL24/MEN1703 conducted in rats and dogs. The dog was the more sensitive species and the observations from the repeat dose dog GLP toxicology study form the basis for the rationale for the FIH starting dose.

This FIH study initially employed an accelerated dose escalation design for the first 4 cohorts, in which the starting dose was 25 mg in the first cohort (1 patient, in the absence of unacceptable toxicity), followed by a dose of 50, 75 and 100 mg in Cohorts 2, 3 and 4, respectively (1 patient per cohort, in the absence of unacceptable toxicity). Thereafter, dose escalation was to proceed according to a conventional 3 + 3 design with successive cohorts having dose increments of 50% or less.

The 25, 50, 75 and 100 mg doses in humans were supported by the non-clinical toxicology findings in animals. Rats and dogs were administered daily doses of SEL24/MEN1703 for two 14-day cycles with one week rest between treatment cycles, followed by a 28-day treatment-free recovery period. This treatment regimen mimics that to be utilized in the first-in-human clinical study in patients with AML.

Doses of 10, 25 and 50 mg/kg (human equivalent dose [HED] of 60, 150 and 300 mg/m^2, respectively) were administered to rats with no significant toxicity findings. Since no MTD was achieved, the rat was considered the less sensitive species.

Doses of 5, 10 and 20 mg/kg (HED of 100, 200 and 400 mg/m^2, respectively) were administered to dogs. The dog was considered the more sensitive species since the 20 mg/kg SEL24/MEN1703 dose resulted in severe clinical signs leading to early termination of 3 out of 12 animals.

Following a four-week recovery period, SEL24/MEN1703-related findings were reversible in all dose groups. Based on the findings in dogs, the NOAEL was 5 mg/kg and the highest non-severely toxic dose (HNSTD) was 10 mg/kg.

As shown in the tables below, the HED of the NOAEL in dogs is 170 mg, based on a human BSA of 1.7 m^2. Per the ICH S9 guidance, an appropriate human starting dose would be 50 mg, which is 1/6th the HNSTD in dogs. This study commenced with a lower starting dose of 25 mg. Doses of 25

mg through 100 mg remain well below the HED of the NOAEL in dogs and are also below the NOAEL and the lowest safe dose tested in rats.

**Table 6: Human rationale based on dog toxicology studies**

SEL24/MEN1703 dose level in dogs (mg/kg/d)	Human equivalent dose (HED)	HED in mg, based on 1.7 m  BSA
5 (NOAEL)	100 mg/m  /d	170 mg
10 (HNSTD)	200 mg/m  /d	340 mg
20 (toxic dose)	400 mg/m  /d	680 mg

**Table 7: Human dose rationale based on rat toxicology studies**

SEL24/MEN1703 dose level in rats (mg/kg/d)	Human equivalent dose (HED)	HED in mg, based on 1.7 m  BSA
10 (safe dose)	60 mg/m  /d	102 mg
25 (NOAEL)	150 mg/m  /d	255 mg
50 (safe dose with reversible SEL24/MEN1703-related findings)	300 mg/m  /d	510 mg

The first patient to be treated with SEL24/MEN1703 commenced dosing on 15 March 2017. As of 06 October 2017, eight patients had been dosed with SEL24/MEN1703 at the dose levels described in Table 8.

**Table 8: CLI24-001 Patient Disposition up to clinical hold (all patients treated with non-formulated IMP)**

Cohort	1	2	3	4	5
SEL24/MEN1703 Dose Level	25 mg	50 mg	75 mg	100 mg	150 mg
N	2*	1	1	1	3
DLT	1	0	0	0	2

\*One patient not included in the dose-determining population

Accelerated titration design had continued through to Cohort 4. At the 150 mg dose level (the first cohort to be enrolled following the 3+3 design), DLTs were reported in 2 patients (another patient experienced a DLT event at 25 mg dose level). The occurrence of these two events meeting the DLT definition at the 150 mg dose level led to an adjustment of the dose escalation plan for this study, whereby SEL24/MEN1703 was more thoroughly evaluated following a “3+3” design.

The subsequent restarting dose level of 50 mg (Cohort 2) following a 3+3 design was selected, also supported by the PK data obtained that far during the CLI24-001 study: the total (AUC) and maximum ( $C_{max}$ ) exposure of SEL24/MEN1703 observed in the patients were within, or slightly exceeding the toxicological coverage established in dog at the dose of 5 mg/kg, which was defined as the HNSTD. After single and repeat dose administration of SEL24/MEN1703 25 mg and 50 mg,  $C_{max}$  and  $AUC_{(0-t)}$  observed in human were more than 11 and 9 times lower than those observed in dogs at the HNSTD, respectively. Overall, the PK results obtained that far in human confirmed that SEL24/MEN1703 exposure at 25 mg and 50 mg is below 1/6 of the exposure obtained at the HNSTD defined in dog (i.e. the most sensitive toxicological species). Moreover, it is noted that the dog is a relevant species also from a metabolic point of view, with the M3 metabolite similarly identified as the main metabolite in human and canine plasma. In a dedicated 10-day toxicology study in the dog (treated at 10, 30 and 60 mg/kg), the parent drug and the M3 metabolite were measured in plasma: the presence of M3 metabolite was confirmed and, at 10 mg/kg, it was double and one third compared to parent drug in the male and female animals, respectively.

As of today, 48 patients were dosed with SEL24/MEN1703 at the doses levels described in Table 9, including 30 patients treated at the RD of 125 mg:

**Table 9: CLI24-001 Patient Disposition**

Cohort	1	2	3	4	4F	4b	5
SEL24/MEN1703 Dose Level	25 mg	50 mg	75 mg	100 mg	100 mg formulated	125 mg	150 mg
Number patients treated with non-formulated IMP	2*	3	3	3	0	0	3
Number patients treated with Formulated IMP	0	0	0	0	3	30*	1
DLT	1	0	0	0	0	1	3

\*One patient not included in the dose-determining population

Since 3 patients (out of 4) treated at 150 mg experienced DLT, the 125 mg dose level, already shown to be tolerable in 6 DLT evaluable patients, was determined to be the RD.

### 1.5. Safety Guidance Information for Investigators

Throughout the study, Investigators should refer to the current edition of the Investigator's Brochure (IB) for a full review of the potential risks associated with treatment with SEL24/MEN1703 and details of expected AEs.

Based on available safety data, administration of SEL24/MEN1703 may be associated with the potential risk of **fatal thrombosis** and **severe hepatotoxicity**. In addition, hypophosphatemia has occurred at the 25, 50, 75, and 150 mg dose levels. Please refer to [Section 6.9.1](#) for further guidance on the management of this latter event.

No other particular risks have been identified for SEL24/MEN1703 according to available clinical data. Nevertheless, results from non-clinical data do not allow to exclude the potential phototoxic effect of MEN1703. To this end, new safety measures - Inclusion of photosensitivity/phototoxicity

preventive measures – have been implemented in previous Clinical Trial Protocol Versions 11.2 and 11.3. Please refer to [Section 6.8](#) for further guidance on the prevention and management of this event.

### Risk Benefit Assessment for COVID-19 pandemic

There is currently an outbreak of respiratory disease (COVID-19) caused by a novel coronavirus SARS-CoV-2 that was first detected in Wuhan City, Hubei Province, China in 2019. This new virus has rapidly spread across the globe causing the World Health Organization (WHO) to declare a pandemic situation on March 12, 2020. In response to the pandemic, the health authorities have issued recommendations on the further conduct of clinical studies. Accordingly, risk assessments of involvement in the trial with added challenges due to COVID-19 and mitigation measures need to be taken into consideration in all clinical studies to protect subjects, site staff and the society as a whole.

In this phase I/II clinical trial for heavily pre-treated relapsed or refractory AML patients the eligibility will be evaluated by the treating physician/PI after individual assessment that the clinical benefit of the investigational product will outweigh the risk of contracting the SARS-CoV-2 infection without compromising the safety of the subjects.

Measures to mitigate the additional risks caused by COVID-19 are:

- Current national laws and local recommendations for prevention of pandemic will be strictly adhered.
- Subjects will be encouraged to strictly follow local mitigation recommendations (e.g. social distancing, use of mask, etc.).
- Access to clinical site will be granted according to local COVID-19 control measures.
- Based on the local circumstances, to be reassessed on an ongoing basis, additional measures will be considered for implementation including:
  - Interruption or slowing down of recruitment of new trial participants;
  - Postponement of activation of sites that have not yet been initiated;
  - Transfer of trial participants to investigational sites away from risk zones, or closer to their home;
  - IMP re-distribution among sites, in case of shortage of study drug;
  - Safety laboratory tests to be performed at local laboratory or participant's home, in case the trial participants cannot reach the site;
  - Remote consent could be collected (when applicable as per local policy).

## 2. STUDY OBJECTIVES

**Table 1: Part 1 Study Objectives and Endpoint (Assessment)**

Objective	Endpoint (Assessments)
Primary:	

 
To estimate the MTD or MAD and determine the RD of SEL24/MEN1703 for Part 2
 
	
 
DLT evaluation at the end of one treatment cycle for each dose level
 

Secondary:	

 
To assess the safety and tolerability of SEL24/MEN1703
 
To assess anti-leukemic activity of SEL24/MEN1703
 
To evaluate the PK profile of SEL24/MEN1703 and its metabolites as appropriate
 
	
 
The number and frequency of AEs, safety laboratory, vital signs and ECG assessments
 
Assessment of bone marrow and peripheral blast % and other assessments of clinical benefit including ORR (CR, CRi, CRh and MLFS), PR rate, DoR, RFS, EFS and OS
 
Assessment of PK variables, including <math>C_{max}</math>, AUC and <math>t_{1/2}</math>
 

Exploratory:	

 
To assess the PD activity of SEL24/MEN1703
 
To assess the genetic profile of AML cells
 
	
 
Flow cytometry assessment of relevant biomarkers (e.g. pS6)
 
Analysis of relevant mutations in peripheral blasts and bone marrow by using Next Generation Sequencing and/or qRT-PCR
 

**Table 2: Part 2 Study Objectives and Endpoint (Assessment)**

Objective	Endpoint (Assessments)
Primary:	

 
To further characterize the safety profile of single agent SEL24/MEN1703
 
	
 
The number and frequency of AE, safety laboratory, vital signs and ECG assessments
 

Secondary:	

 
To assess anti-leukemic activity of single agent SEL24/MEN1703
 
To evaluate the PK profile of SEL24/MEN1703 and its metabolites, as appropriate
 
	
 
Assessment of bone marrow and peripheral blast % and other assessments of clinical benefit including ORR (CR, CRi, CRh and MLFS), PR rate, DoR, RFS, EFS, OS, transfusion conversion rate, transfusion maintenance rate, HSCT rate
 
Assessment of PK variables, including <math>C_{max}</math>, AUC and <math>t_{1/2}</math>
 

Exploratory:	

 
To assess the PD activity of SEL24/MEN1703
 
	
 
Flow cytometry assessment of relevant biomarkers (e.g. pS6)
 

Objective	Endpoint (Assessments)

• To assess the genetic profile of AML cells

	

• Analysis of relevant mutations in peripheral blasts and bone marrow by using Next Generation Sequencing and/or qRT-PCR

### 3. SELECTION CRITERIA

#### 3.1. Inclusion Criteria

Patients are eligible to be included in study if they meet all of the following criteria:

1. Patient with diagnosis of AML (i.e.  $\geq 20\%$  blasts in bone marrow or peripheral blood) harboring IDH1 or IDH2 mutation (as per local assessment).
2. Provide written informed consent prior to Screening.
3. Male or female patients, age  $\geq 18$  years old.
4. Patient has no standard therapeutic options available (including IDH inhibitors where approved) and has:
  - a) Relapsed AML unsuitable for intensive chemotherapy;
  - b) Primary refractory AML unsuitable for intensive chemotherapy;

**Clarification note:** Patients naïve to IDH inhibitors are eligible ONLY if no IDH inhibitors are approved/available in the country/site where they are enrolled.

5. ECOG Performance Status 0, 1 or 2.
6. Adequate organ function at Screening, including:
  - e) Aspartate aminotransferase (AST) and alanine aminotransferase (ALT)  $\leq 2.5$ X the upper limit of normal (ULN);
  - f) Total bilirubin  $\leq 2$ X ULN;
  - g) Creatinine clearance  $\geq 40$  mL/min (Cockcroft-Gault formula) (see [Appendix B](#));
  - h) Left ventricular ejection fracture (LVEF)  $\geq 40\%$  as per local assessment practice.
7. A female of childbearing potential, defined as any female who has experienced menarche and who has not undergone successful surgical sterilization or is not postmenopausal (i.e. has serum follicle stimulating hormone level  $\geq 30$  IU/L in the absence of hormone replacement therapy, or complete absence of menses for at least 12 consecutive months which is not due to medication), must have a negative pregnancy test within 7 days prior to receiving study drug.
8. Sexually active male or female patients of childbearing potential are eligible providing that:

Female:

- Agrees to use an effective method of birth control as applicable per local law that both results in a Pearl index  $< 1$  and is considered highly effective as defined by the Clinical Trial Facilitation Group (e.g. combined estrogen and progestogen containing hormonal contraception, progestogen-only hormonal contraception, intrauterine device, intrauterine hormone-releasing system, vasectomized partner, total sexual abstinence or bilateral tubal occlusion)\*.
- Undergoes a pregnancy test at Day 1 of each treatment cycle and after the end of relevant systemic exposure (30 days from the last study drug administration).

Male:

- Agrees to use an effective contraceptive method (condom) during treatment and until the end of relevant systemic exposure. Females of childbearing potential that are partners of male study participants have to observe the same birth control indications that apply to female participants.

*\*Hormonal contraceptives are allowed as pre-clinical evaluation of SEL24/MEN1703 confirmed a low interaction between SEL24/MEN1703 and the most common active principles used for this purpose.*

### 3.2. Exclusion Criteria

Patients are not eligible to be included in study if they meet any of the following criteria:

1. Received anti-cancer treatments (including cytotoxic chemotherapy, radiotherapy, hormonal therapy, biologic, immunotherapy or investigational drugs) within 14 days or 5 half-lives (whichever is longer) before the first dose of study drug.
2. Prior treatment with a PIM inhibitor.
3. Hyperleukocytosis (leukocytes  $>30 \times 10^9/L$ ) immediately prior to the first dose of study drug and/or clinical concerns of leukostasis.  
**Note:** *Patients may undergo leukapheresis according to routine practice before the first dose of study drug; where hydroxyurea is used prior to receiving study drug, it may be continued up to Cycle 1, Day 21, although Investigators are asked to stop treatment prior to the first dose of study drug or before Day 7, wherever possible.*
4. Clinically significant active central nervous system (CNS) leukemia.  
**Note:** *Previously treated and controlled CNS leukemia and ongoing standard CNS prophylaxis (e.g. with intrathecal cytarabine) is acceptable.*
5. Patients who have undergone major surgery within 1 month prior to first dose of study drug.
6. Hematopoietic stem cell transplant within 4 months of first dose of study drug.
7. Requires systemic immune-modulating therapy (regardless of dose) for the prophylaxis or treatment of GVHD.
8. Evidence of ongoing and uncontrolled systemic bacterial, fungal, or viral infection, with the exception of patients with documented Grade CTCAE  $\leq 2$  infections with evidence of improvement or without evidence of worsening infection.
9. Known positive serology for human immunodeficiency virus (HIV).
10. Ongoing drug-induced liver injury, known chronic active hepatitis C (HCV) infection, known chronic active hepatitis B (HBV) infection, alcoholic liver disease, non-alcoholic steatohepatitis, primary biliary cirrhosis, extrahepatic obstruction cause by cholelithiasis, cirrhosis of the liver, or portal hypertension. Participants with history of chronic HBV and HCV infection are eligible if disease is stable and sufficiently controlled as per investigator's judgment.
11. Ongoing drug-induced pneumonitis.
12. Ongoing inflammatory bowel disease.
13. Pregnancy or breastfeeding.
14. Concurrent participation in another therapeutic clinical study.

15. Ongoing toxicity from any prior anti-cancer therapy that has not resolved to Grade 1 or less prior to the first dose of study drug.
16. Received an agent known to be a sensitive CYP2D6 substrate or a CYP2D6 substrate with a narrow therapeutic range, a strong or moderate CYP2D6 inhibitor, or a BCRP inhibitor within 7 days or a period corresponding to 4-5 half-lives of the agent, prior to the first dose of study drug.
17. Cardiac dysfunction defined as myocardial infarction within 6 months of study entry, New York Heart Association (NYHA) Class III or IV heart failure, uncontrolled dysrhythmias or poorly controlled angina.
18. Are receiving any active treatment for thrombosis.
19. History of serious ventricular arrhythmia (e.g. VT or VF,  $\geq 3$  beats in a row), or QT interval corrected for heart rate (QTc)  $\geq 480$  ms.  
*Note: QTc values up to 500 ms will be acceptable where patient's medical history e.g. bundle branch block, is known to cause mild QTc prolongation and the condition is well controlled.*
20. Any disease, syndrome or condition which may affect significantly drug intake via oral route.
21. Any other prior or current medical condition, intercurrent illness, surgical history, physical or 12-lead electrocardiogram (ECG) findings, laboratory abnormalities, or extenuating circumstance (e.g. alcohol or drug addiction) that, in the investigator's opinion, could jeopardize patient safety or interfere with the objectives of the study.

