**Footnotes:**

- 1 A pregnancy test is required within 7 days prior to receiving study drug. Pregnancy test may be alternatively carried out at C1D1 visit prior to first SEL24/MEN1703 administration; results of the test should be available prior to receiving study drug. Additionally, a pregnancy test is required on the first day of each study cycle and at the Final Study Visit. If the Final Study Visit is performed before 30 days has elapsed from the last study drug administration, the pregnancy test shall be postponed when 30 days (+7 d tolerance) from the last study drug intake is elapsed (i.e. when no relevant drug systemic exposure is expected). A negative pregnancy test may be confirmed by urine or blood test. Where a urine test is positive or equivocal, a blood test must be performed to confirm the result. Patients requiring confirmation of post-menopausal status will have FSH levels assessed at Screening.
- 2 Vital signs include temperature, systolic blood pressure, diastolic blood pressure, heart rate and respiratory rate.
- 3 Physical examination includes height and weight at Screening and only weight at the start of each cycle. After Screening, further assessments may be symptom-directed.
- 4 For complete list of Clinical chemistry, Hematology, Coagulation, and Lipid profile parameters please refer to [Appendix E](#). Coagulation parameters may be assessed from the Hematology sample. Should a patient develop coagulation abnormalities at any point during the study, a comprehensive evaluation of coagulation abnormalities will be performed immediately which may include, but not be limited to repeat PT/INR, APTT, fibrinogen, D-dimer, plus a peripheral blood smear, thrombin time, to be evaluated by the Investigator in conjunction with the patient's medical history, a physical examination and concomitant medication review. Repeat testing may be performed as clinically indicated, which may include additional parameters or time-points (please also refer to [Appendix E](#)).
- 5 Assessment of blasts in peripheral blood will be carried out at Screening, C1 D1 pre-dose, C1 onwards at D14 (or last day of dosing in each cycle; -2 d tolerance from C3 onwards), and FSV. This assessment may be performed from the Hematology sample.
- 6 At C1 D1, the electrocardiogram assessment will be carried out pre-dose and at 4-6 h post dose.

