7.2.2. Key definitions

Baseline values

The baseline value of an assessment is defined as the last available (non-missing) value before or on the date of first administration (Day 1) for Cycle 1.

Adverse Events (AEs)

An AE is any untoward medical occurrence in a patient (or a clinical investigation subject), receiving a medicinal product and which does not necessarily have a causal relationship with the treatment. Therefore an AE can be any unfavourable and unintended sign (including an abnormal clinically significant laboratory finding), symptom, or disease temporally associated with the use of a medicinal (investigational) product, whether or not related to the medicinal (investigational) product. All identified AEs are recorded and described on the appropriate AE page of the eCRF, except for those events occurring prior to the first dose of study medication, which are recorded on the Medical History eCRF page.

Adverse Drug Reactions (ADRs)

Untoward and unintended responses to an Investigational Medicinal Product (IMP) related to any dose administered. The definition covers also medication errors and uses outside what is foreseen in the protocol, including misuse and abuse of the product. The definition implies a 'reasonable possibility of a causal relationship between the event and the IMP. This means that there are facts (evidence) or arguments to suggest a causal relationship.

All AEs (including SAEs) have to be accurately recorded on the AE page of the patient's eCRF. Each event will be graded for severity using the classifications of NCI CTCAE v4.03. For events not addressed in the NCI CTCAE v4.03, classifications will be performed according to the following grading:

- Mild (Grade 1) - Mild; asymptomatic or mild symptoms; clinical or diagnostic observations only; intervention not indicated;
- Moderate (Grade 2) - Moderate; minimal, local or noninvasive intervention indicated; limiting age-appropriate instrumental activity of daily living;
- Severe (Grade 3) - Severe or medically significant but not immediately life-threatening; hospitalization or prolongation of hospitalization indicated; disabling; limiting self-care activity of daily living;
- Life-threatening (Grade 4) - Life-threatening consequences; urgent intervention indicated.

- Death (Grade 5) - Related to adverse event.

Serious Adverse Event (SAE) / Serious Adverse Drug Reaction (SADR)

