12.1. Efficacy analysis

The Overall Survival (OS) is calculated as:

- In case of all-cause death:
 $OS = date\ of\ death - date\ of\ first\ study\ drug\ administration + 1;$
- In case of censored information not for drop-out:
 $OS = date\ of\ end\ of\ observation\ period\ (i.e.\ study\ end / end\ of\ survival\ follow-up) - date\ of\ first\ study\ drug\ administration + 1;$
- In case of censored information for drop-out:
 $OS = last\ date\ known\ alive - date\ of\ first\ study\ drug\ administration + 1.$

The Relapse Free Survival (RFS) is calculated as:

- In case of relapse or all-cause death:
 $RFS = date\ of\ relapse\ or\ death\ (whichever\ comes\ first) - date\ of\ first\ CR,\ CRi,\ CRh\ or\ CR_{MRD-} + 1;$
- In case of censored information:
 $RFS = date\ of\ last\ relapse-free\ disease\ assessment - date\ of\ first\ CR,\ CRi,\ CRh\ or\ CR_{MRD-} + 1.$

The Event Free Survival (EFS) is calculated as:

- In case of relapse, treatment failure or all-cause death:
 $EFS = date\ of\ relapse,\ disease\ progression,\ treatment\ failure\ (failure\ to\ achieve\ CR/CRh/CRi/CR_{MRD-}\ after\ at\ least\ five\ cycles\ of\ treatment)\ or\ death\ (whichever\ comes\ first) - date\ of\ first\ study\ drug\ administration + 1;$
- In case of censored information:
 $EFS = date\ of\ last\ relapse-free/treatment-failure-free/progression-free\ disease\ assessment - date\ of\ first\ study\ drug\ administration + 1.$

The Duration of Response (DoR) is calculated as:

- In case of relapse, progressive disease or death due to progressive disease:
 $DoR = date\ of\ relapse\ of\ any\ type/progressive\ disease/death\ due\ to\ progressive\ disease - date\ of\ first\ CR,\ CRi,\ CRh,\ CR_{MRD-},\ MLFS\ or\ PR + 1;$
- In case of censored information:
 $DoR = date\ of\ last\ relapse-free\ disease\ assessment - date\ of\ first\ CR,\ CRi,\ CRh,\ CR_{MRD-},\ MLFS\ or\ PR + 1.$

No formal statistical analysis will be performed on anti-leukemic parameters.

Anti-leukemic activity data will be collected throughout Part 1 and Part 2 and will be summarized by cohort, by dose and overall.

Measures of anti-leukemic activity will be computed on both safety and efficacy populations and they will include:

- Changes (absolute and %) in pre- and post-treatment levels of leukemic blasts in the peripheral blood and/or bone marrow;
- Number and percentages of patients who reported as best overall response one of the following: CRM RD-, CR, CRh, CRi, MLFS, PR, SD, PD;
- Duration of response (DoR);

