13.2.3. Figures

Figures

- Figure 1: Overall Mean and Median timecourse – ALT ($\mu\text{kat/L}$)
- Figure 2: Overall Mean and Median timecourse – AST ($\mu\text{kat/L}$)
- Figure 3: Overall Mean and Median timecourse – Blasts ($10^9/\text{L}$)
- Figure 4: Overall Mean and Median timecourse – Hemoglobin (g/L)
- Figure 5: Overall Mean and Median timecourse – Lymphocytes ($10^9/\text{L}$)

Figure 6: Overall Mean and Median timecourse – Neutrophils ($10^9/L$)
Figure 7: Overall Mean and Median timecourse – Platelet ($10^9/L$)
Figure 8: Overall Mean and Median timecourse – White Blood Cells ($10^9/L$)
Figure 9: Overall Mean and Median timecourse – Total Bilirubin ($\mu mol/L$)
Figure 10: Overall Mean and Median timecourse – Direct Bilirubin ($\mu mol/L$)
Figure 11: Overall timecourse – ALT ($\mu kat/L$)
Figure 12: Overall timecourse – AST ($\mu kat/L$)
Figure 13: Overall timecourse – Blasts ($10^9/L$)
Figure 14: Overall timecourse – Hemoglobin (g/L)
Figure 15: Overall timecourse – Lymphocytes ($10^9/L$)
Figure 16: Overall timecourse – Neutrophils ($10^9/L$)
Figure 17: Overall timecourse – Platelet ($10^9/L$)
Figure 18: Overall timecourse – White Blood Cells ($10^9/L$)
Figure 19: Overall timecourse – Total Bilirubin ($\mu mol/L$)
Figure 20: Overall timecourse – Direct Bilirubin ($\mu mol/L$)
Figure 21: Individual MEN1703 PK concentration-time profiles (separate)
Figure 22: MEN1703 PK concentration-time profiles (mean values with error bars)
Figure 23: Boxplots of MEN1703 C_{max} and AUC_{24} at Cycle 1 Day 1 and at Cycle 1 Day 14, versus dose
Figure 24: Individual MET3 PK concentration-time profiles (separate)
Figure 25: MET3 PK concentration-time profiles (mean values with error bars)
Figure 26: Boxplots of MET3 C_{max} and AUC_{24} at Cycle 1 Day 1 and at Cycle 1 Day 14, versus dose

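### The Cycle 1 peripheral-blast change reported as SEL24/MEN1703 activity can be shifted in either direction by permitted hydroxyurea, and SAP 12.1 does not identify the exposed patients

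*Protocol*

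**What the plan says.** - **Cytoreduction allowed.** Protocol 3.2, note to criterion 3 (repeated in the synopsis): "where hydroxyurea is used prior to receiving study drug, it may be continued up to Cycle 1, Day 21". The same note adds "Investigators are asked to stop treatment prior to the first dose of study drug or before Day 7, wherever possible", and on leukapheresis, "Patients may undergo leukapheresis according to routine practice before the first dose of study drug".
- **Blast sampling.** Protocol Table 5, footnote 5: "Assessment of blasts in peripheral blood will be carried out at Screening, C1 D1 pre-dose, C1 onwards at D14", and again at the Final Study Visit.
- **Baseline.** SAP 7.2.2 takes the "last available (non-missing) value before or on the date of first administration (Day 1) for Cycle 1". For peripheral blasts this is normally the C1D1 pre-dose count.
- **Measure.** SAP 12.1 lists first among its activity measures "Changes (absolute and %) in pre- and post-treatment levels of leukemic blasts in the peripheral blood and/or bone marrow", on both the safety and efficacy populations, by cohort, dose and overall. Protocol 8.9 lists the same measure.
- **Objective served.** Protocol Table 2, secondary objective: "To assess anti-leukemic activity of single agent SEL24/MEN1703".
- **Display.** SAP 13.2.3 includes "Figure 3: Overall Mean and Median timecourse – Blasts" and, as Figure 13, a second overall blast time-course.
- **Handling of hydroxyurea or leukapheresis.** None. The SAP names neither. Section 11.3 uses observed cases throughout, section 12.2 marks subgroup analyses as not applicable, and concomitant medication appears in Table 1.7 and Listing 4.8 without a link to blast counts.

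**The concern.** This is an uncontrolled study, so activity is read directly from descriptive summaries, and no comparator arm absorbs the effect of other cytoreduction. The protocol itself recognises that hydroxyurea acts on this variable: the comment on progressive disease in Appendix D mentions its use to lower blast counts. Exclusion criterion 1 requires washout of other anti-cancer treatment, while criterion 3 lets hydroxyurea run into the treatment period. An early fall or rise in blasts may therefore be credited to SEL24/MEN1703, or held against it, when part of it comes from starting, continuing or stopping hydroxyurea. At stake is how the earliest activity signal in a small cohort is read. No test, error rate or sample size depends on it.

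**Working it through.** The plan states no figure to reproduce: activity is descriptive and SAP section 8 makes no formal sample size calculation. The check has four steps.

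**1. Timing (nominal days, 21-day cycles).**

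| Point | Study day | Against the day 21 limit |
|---|---|---|
| C1D14 blasts | 14 | inside, by 7 days |
| C2D14 blasts | 21 + 14 = 35 | 14 days after |
| C3D1 marrow | 2 × 21 + 1 = 43 | 22 days after |

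C1D14 is the only scheduled post-dose blast count in Cycle 1. Neither document names a C1D1-to-C1D14 contrast; it follows from the schedule and the baseline rule.

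Following the request to stop early does not remove the problem. A patient who stops after C1D1 but before Day 7 has been off hydroxyurea for at least 14 − 7 = 7 days at the Day 14 sample, but the baseline was drawn on it.

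**2. Direction.**

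| Pattern | Baseline (C1D1) | Day 14 | Effect on apparent change |
|---|---|---|---|
| Hydroxyurea started shortly before C1D1, continued | effect partial | effect larger | downward |
| Hydroxyurea at steady effect before C1D1, continued | already included | unchanged | little or none |
| Hydroxyurea stopped after C1D1 | lowered | effect wearing off | upward |
| Leukapheresis before the C1D1 sample | lowered | possible regrowth | none or upward |
| Leukapheresis after Screening, C1D1 count missing | not lowered (Screening used) | may still be lowered | none or downward |

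**3. Downward size (assumed inputs).** Let d be the true drug reduction, h the share of patients in the first pattern, and e the further reduction from hydroxyurea after C1D1. Unexposed patients end at (1 − d) of baseline and exposed patients at (1 − d)(1 − e), so

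mean % change = −100 × [d + (1 − d) × h × e].

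| d | h | e = 0.2 | e = 0.4 | e = 0.6 |
|---|---|---|---|---|
| 0 | 0.10 | −2.0 | −4.0 | −6.0 |
| 0 | 0.25 | −5.0 | −10.0 | −15.0 |
| 0 | 0.50 | −10.0 | −20.0 | −30.0 |
| 0.3 | 0.10 | −31.4 | −32.8 | −34.2 |
| 0.3 | 0.25 | −33.5 | −37.0 | −40.5 |
| 0.3 | 0.50 | −37.0 | −44.0 | −51.0 |

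In a cohort of 20, h = 0.10, 0.25 and 0.50 are 2, 5 and 10 patients.

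**4. Upward size (assumed inputs, no drug effect).** If leukapheresis removed a fraction L before baseline and a share g of that has returned by Day 14, the patient's change is 100 × g × L / (1 − L).

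- L = 0.3: 0%, +21.4% and +42.9% for g = 0, 0.5 and 1.
- L = 0.5: 0%, +50% and +100%.

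The same formula applies to hydroxyurea stopped after C1D1, with L read as the suppression present at baseline. If the C1D1 count is missing and Screening precedes the procedure, the change is −100 × L × (1 − g): from 0% to −30% for L = 0.3 and from 0% to −50% for L = 0.5.

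**The case against.** The best defence has several parts, and much of it stands.

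- **Leukapheresis.** A reader might infer that it inflates the apparent fall. With the usual C1D1 baseline it cannot, because it is allowed only before dosing; it lowers the baseline and, with regrowth, works against the drug. The exception is a missing C1D1 count.
- **Established hydroxyurea.** The note covers continuation only, so a settled effect is already partly in the baseline. That narrows the downward bias without removing it, and it is the reason stopping creates the upward one.
- **Other endpoints.** A reader might infer that the single-agent question cannot be answered. The documents do not support that: ORR, PR rate, DoR, RFS, EFS and OS serve the same objective, and response needs marrow criteria. Marrow may be taken before C3D1 when blood results suggest response, so a hydroxyurea-driven fall could contribute to that trigger, but the marrow criteria still apply.
- **White cell counts.** They are not a listed activity measure, they appear among general laboratory plots, and hematology is sampled more often (C2D1 is day 22). The point does not extend to them.
- **Data already listed.** Listings 4.7 and 4.8 let a diligent reader match exposure by hand. The summary and figures still give no such indication.
- **Selection.** Replacing the main summary with hydroxyurea-free patients would condition on post-baseline management. Patients with proliferating disease are likelier to stay on hydroxyurea, so that subset could favour the drug. This stands, and the fix below respects it.

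**Conclusion.** The point holds as a cheap improvement to one descriptive measure under a secondary objective. The permitted hydroxyurea period covers the only scheduled Cycle 1 post-dose blast count, that change is reported as SEL24/MEN1703 activity, and no output identifies exposed patients. The defensible wording is that the early change *can* be biased, downward or upward. That it *does* largely measure hydroxyurea is a stronger reading without support, because neither document gives the frequency, timing or tapering of use.

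The sizes above rest entirely on assumed h, e, d, L and g. With no drug effect they run from −2% to −30% for the cohort mean; individual upward shifts after leukapheresis run from 0% to +100%. The downward figures also assume that all of e arises after C1D1, so they are upper limits for patients whose hydroxyurea effect was partly established. Scheduled values from C2D14 onward, and the C3D1 marrow in particular, are much less exposed.

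The quoted criterion is that of protocol Version 12, whose eligibility text describes the IDH-mutant cohort. Whether earlier cohorts had the same allowance is not shown. A flag built from recorded dates works in either case.

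**What to change.** In SAP 12.1:

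1. Keep the all-patient blast-change summary as the main one and state which baseline visit was used.
2. Derive from eCRF dates a flag for hydroxyurea use between baseline and each blast sample, and a flag for leukapheresis shortly before baseline. Fix the leukapheresis interval in the SAP, since the documents give no figure.
3. Beside the main summary, show the change in unexposed patients as a sensitivity summary, with its N. Note that this subset is smaller and selected on post-baseline management.
4. Mark exposed patients or visits on Figure 13, taken here to be the individual blast time-course.
5. Flag any response whose supporting blood counts were drawn on hydroxyurea.

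The cost is one SAP paragraph and a date merge. Protocol 6.9.1 requires concomitant medication from 30 days before first dose to be recorded, and SAP 11.4 summarises prior and concomitant procedures. Two limits remain. Recording of dose changes is optional under 6.9.1, so the flag may show use but not a taper. A patient who stopped just before C1D1 counts as unexposed although the baseline may still be lowered. No change is needed to the hydroxyurea allowance or to the white-cell safety outputs.
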